## **Appendix 1. Allowed and Disallowed Treatments for JIA**

### **Allowed DMARDs:**

The following DMARDs are allowed in doses consistent with local standards of care:

- Methotrexate may be taken orally or parenterally at doses not to exceed 25 mg/wk or 20 mg/m^2/week [whichever is lower]). Participants must have taken MTX for ≥3 months and be at a stable dose for at least 6 weeks before baseline and should be on a stable dose for the duration of the study [open-label run-in and double-blind phases]). Subjects taking methotrexate must be taking folic acid or folinic acid in accordance with local standards.

### **Allowed Treatments for Psoriatic Arthritis:**

For subjects with PsA, the following topical treatments for psoriasis are allowed:

- Non-medicated emollients for use over the whole body;
- Topical steroids including hydrocortisone and hydrocortisone acetate ≤1% for the palms, soles, face, and intertriginous areas only;
- Tar, salicylic acid preparations, and shampoos free of corticosteroids are permitted only for the scalp.

### **Disallowed Biologic and Non-Biologic DMARDs:**

The following biologic agents and DMARDs are disallowed at any time during this study. If a subject requires (in the opinion of the investigator) treatment with one of these agents, the subject should be discontinued from the study:

- Leflunomide (Arava®) must have been discontinued 8 weeks prior to the first dose of study drug if no elimination procedure is followed;
- Anakinra (Kineret®), Enbrel (Etanercept®): Discontinued for 4 weeks prior to the first dose of study drug;
- Canakinumab (Ilaris®): Discontinued for 18 weeks prior to the first dose of study drug;
- Adalimumab (Humira®): Discontinued for 6 weeks prior to first dose of study drug;
- Infliximab (Remicade®): Discontinued for 8 weeks prior to the first dose of study drug;
- Golimumab (Simponi TM): Discontinued for 10 weeks prior to the first dose of study drug;

- Abatacept (Orencia®), Tocilizumab (Actemra®), Certolizumab pegol (Cimzia®): Discontinued for 12 weeks prior to first dose of study drug;
- Rituximab (Rituxan®) or other selective B lymphocyte depleting agents (either marketed or investigational): Discontinued for 1 year prior to the first dose of study drug and if CD19/20+ counts are normal by FACS analysis.

**Other Disallowed Agents:**

- Bucillamine, mizoribine, sulfasalazine, d-penicillamine, azathioprine, chloroquine, hydroxychloroquine, cyclosporine, tacrolimus, and staphylococcal protein A immuno-absorbant pheresis columns (eg, PROSORBA® device/column) must be discontinued for 4 weeks prior to first dose of study drug;
- Auranofin (oral gold), aurothioglucose (injectable gold), aurothiomalate (injectable gold) must be discontinued for 8 weeks prior to first dose of study drug.

**Disallowed Treatments for PsA:**

For subjects with PsA, oral and topical medications and alternative treatments that could affect psoriasis are prohibited. This includes:

- Topical corticosteroids (except those described in the “[Allowed Treatments for Psoriatic Arthritis](#)” section of [Appendix 1](#)), tars, keratolytics, anthralin, vitamin D analogs, and retinoids which must be discontinued at least 2 weeks prior to first dose of study drug;
- Ultraviolet B (UVB) (narrowband or broadband) phototherapy that must be discontinued at least 2 weeks prior to first dose of study drug;
- Psoralens + ultraviolet A (UVA) phototherapy (PUVA) must be discontinued at least 4 weeks prior to first dose of study drug.

**Disallowed Investigational Drugs:**

- **Investigational NSAIDs:** Any experimental non-steroidal anti-inflammatory drug (NSAID), including selective COX-2 inhibitors, must be discontinued for 4 weeks prior to the first dose of study drug.
- **Other Investigational Drugs:** Any other experimental therapy must be discontinued for 6 months or 5 half-lives (whichever is longer) prior to the first dose of study drug.

## Appendix 2. Permitted Adjustments In JIA Therapies

The following adjustments of background medications are allowed for reasons of inadequate efficacy of current treatment. Adjustments for safety reasons may be done at any time, but if this leads to changes in excess of those allowed below, the investigator must receive approval from the Pfizer project team to allow the subject to continue in the trial.

1. NSAIDs/COX-2 inhibitors: dose adjustments may be made, or background NSAID/COX-2 inhibitors may be switched, but should be no more frequently than every 3 months, and should be more than 14 days prior to a study visit.
2. Oral corticosteroid dose should be stable for the duration of the study (open-label run-in and double-blind phases) and not exceed 0.2 mg/kg/day prednisone or equivalent or 10 mg per day, whichever is lower.
3. Methotrexate (MTX) may be administered either orally or parenterally at doses not to exceed 25 mg/wk or 20 mg/m^2/week (whichever is lower) and should remain stable for the duration of the study (open-label run-in and double-blind phases).
4. Intra-articular steroids should be administered in a total dosage of no more than 2 mg/kg (up to 80 mg) of methylprednisolone equivalent every 6 months. No more than two joints should be injected in any given 6 month period and individual joints should not be injected any more frequently than once in a 6-month period. **Injected joints will be considered active joints for the remainder of the study and for efficacy assessments.**

### **Appendix 3. Estimated Glomerular Filtration Rate Calculation**

Bedside Schwartz (Schwartz, 2009) GFR equation will be used to estimate glomerular filtration rate (GFR) from serum creatinine (creatinine method with calibration traceable to IDMS).

$$\text{GFR (mL/min/1.73 m}^2\text{)} = 0.413 \times (\text{Ht} / \text{Scr})$$

Height (Ht) in cm;

Serum creatinine (Scr) in mg/dL;

#### Appendix 4. Prohibited Concomitant Medications

All prohibited drugs require a 4 week (or  $\geq 5$  half-lives, whichever is longer) washout, except:

\* **Amiodarone** half-life averages about 58 days and requires a 290 day washout (5 half-lives).

\*\* **Biologic and Non-Biologic DMARDs** which have specific washout periods are listed in [Appendix 1](#).

NOTE: Topical administration (eg, cutaneous, ophthalmic, or intravaginal) of listed concomitant medications, which are prohibited if administered systemically, is allowed in the study.	
Moderate or Potent CYP3A Inhibitors	Moderate or Potent CYP3A Inducers
HIV antivirals:	efavirenz (Sustiva)
-delavirdine (Rescriptor)	nevirapine (Viramune)
-indinavir (Crixivan)	Barbiturates
-nelfinavir (Viracept)	carbamazepine (Carbatrol, Tegretol)
-ritonavir (Kaletra, Norvir)	modafinil (Provigil)
-saquinavir (Fortovase)	phenobarbital
-atazanavir	phenytoin (Dilantin, Phenytek)
amiodarone (Cordarone, Pacerone)*	rifabutin (Mycobutin)
cimetidine (Tagamet)	rifampin (Rifadin, Rifamate, Rifater)
clarithromycin (Biaxin, Prevpac)	rifapentine (Priftin)
telithromycin (Ketek)	St. John's Wort
clotrimazole	troglitazone (Rezulin)
chloramphenicol	All Investigational Drugs
diethyl-dithiocarbamate	DMARDs
diltiazem (Cardizem, Tiazac)	All Biologics** , such as:
erythromycin	anakinra (Kineret), etanercept (Enbrel),
fluconazole (Diflucan)	adalimumab (Humira), infliximab
fluvoxamine (Luvox)	(Remicade), abatacept (Orencia),
Grapefruit juice and marmalade	canakinumab (Ilaris), tocilizumab
itraconazole (Sporanox)	(Actemra), golimumab (Simponi),
ketoconazole (Nizoral)	rituximab (Rituxan),
mifepristone (Mifeprex, RU486)	Other DMARDs**:
nefazodone (Serzone)	leflunomide, sulfasalazine, d-penicillamine,
norfloxacin (Shibroxin, Noroxin)	bucillamine, mizoribin, azathioprine,
mibefradil	cyclosporine, tacrolimus, auranofin,
verapamil (Calan SR, Covera HS, Isoptin SR, Tarka, Verelan)	aurothioglucose, aurothiomalate,
voriconazole	staphylococcal protein A immuno-absorbant pheresis columns

## Appendix 5. Rescue Therapy

Acetaminophen/paracetamol is allowable as rescue medication if dosed no more than 10-15 mg/kg/dose orally or 15-20 mg/kg/dose rectally (not exceeding 5 doses in 24 hours) for no more than 10 consecutive days. If a subject is already taking stable background doses of acetaminophen/ paracetamol, (s) he may increase the dose up to the maximum dose stated above for up to 10 consecutive days for rescue purposes.

**The following paradigm should be used to determine appropriate opioid rescue therapy:**

***For subjects who are NOT on stable, background opioid therapy:*** any of the following single opioid agents may be given as rescue medication (with or without acetaminophen/ paracetamol) for no more than 10 consecutive days in the following total daily doses:

Morphine	0.2-0.5 mg/kg/dose, up to 15 mg/dose. No more than 5 doses/day.
Hydromorphone (Dilaudid)	0.03-0.08 mg/kg/dose, up to 2 mg/dose. No more than 5 doses/day.
Codeine (Paveral, Tylenol #2 and #3)	0.5-1.0 mg/kg/dose, up to 60 mg/dose. No more than 5 doses a day.
Oxycodone [Roxicodone; Percocet, Tylox]	0.05-0.15 mg/kg/dose, up to 5 mg/dose. No more than 5 doses a day.

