***For subjects who ARE on stable, background opioid therapy:***

- They may NOT add a second opioid agent for rescue;
- If their background medication is 1 of the 4 listed above, they may, within the above maximum total dosage limits, increase the dosage for up to 10 consecutive days for rescue purposes.
- If their background medication is a short acting (half-life <5 hrs) opioid that is not one of those listed above, they may increase the dosage for up to 10 consecutive days (up to a total daily dose which must not exceed the potency equivalent of 30 mg of orally administered morphine for rescue purposes).
- Sustained release opioid formulations (eg, OxyContin®, MS Contin®) and opioids with half-lives greater than 5 hours (eg, methadone, propoxyphene) may NOT be USED for rescue medication or increased for rescue purposes.

Intravenous or intramuscular corticosteroids, biologic response modifiers and DMARDs other than those specified as allowed DMARDs ([Appendix 1](#)) are not allowed during this study. Intra-articular corticosteroids may be given in no more than two joints, in a cumulative dose of no more than 80 mg methylprednisolone or its equivalent in any 6 month study period. Injections should be avoided for 6 weeks before any study visit. Injected joints

will also be considered as having their pre-injection status (tender/painful and swollen) for the remainder of the trial.

Acetaminophen/paracetamol is not permitted as a part of combination products such as over-the-counter “cold remedies” or in combination with opioids if the acetaminophen/paracetamol dose will exceed 2.6 gm/day. Subjects who require rescue for more than 10 consecutive days should be considered for allowed JIA medication adjustments or discontinued from the trial. In addition, subjects should not be dosed with rescue acetaminophen/ paracetamol or opioids during the 24 hours prior to a study visit. Baseline stable acetaminophen/ paracetamol or opioids should NOT be discontinued in advance of study visits.

**Subjects should avoid dosing with rescue intervention within 24 hours prior to a study visit unless indicated for subject safety and individual case management at the discretion of the investigator.**

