##### Deviations Assessed Post-Randomization:

Only protocol deviations that are thought to affect the efficacy of study drug will be considered. Each of the cases will be reviewed by the team and a clinical judgment made in each particular circumstance as to whether efficacy would have been affected in the cases of these specific classes of protocol deviations assessed post randomization:

- Subjects who receive excluded concomitant medications;
- Subjects who interrupt therapy for longer than allowed;
- Subjects who were randomized but took incorrect treatment;
- CCI [REDACTED]
- Subjects whose background medications are changed in violation of protocol, including subjects who use rescue medication in violation of protocol.

Each subject's presence on the list of exclusion from the per-protocol analysis means that there was at least one deviation for that subject clinically judged to effect efficacy.

CCI

CCI

CCI

CCI

CCI

CCI

CCI

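### Appendix 5 labels the opioid rescue limits as daily totals but writes every row per dose, so the two give daily maxima five-fold apart

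*Protocol*

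**What the plan says.** Protocol Appendix 5 (Rescue Therapy) treats two groups separately.

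Subjects not on stable background opioid therapy may take any one of four agents "for no more than 10 consecutive days in the following total daily doses". The rows then read:

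- Morphine: "0.2-0.5 mg/kg/dose, up to 15 mg/dose. No more than 5 doses/day"
- Hydromorphone: "0.03-0.08 mg/kg/dose, up to 2 mg/dose. No more than 5 doses/day"
- Codeine: "0.5-1.0 mg/kg/dose, up to 60 mg/dose. No more than 5 doses a day"
- Oxycodone: "0.05-0.15 mg/kg/dose, up to 5 mg/dose. No more than 5 doses a day"

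Subjects who are on stable background therapy with one of these four agents may raise their dosage for rescue "within the above maximum total dosage limits". If the background agent is a different short-acting opioid, the appendix sets a separate total daily ceiling, "which must not exceed the potency equivalent of 30 mg of orally administered morphine for rescue purposes".

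SAP 9.4, under deviations assessed post-randomization, lists background-medication changes that breach the protocol, "including subjects who use rescue medication in violation of protocol". It says that the team reviews each case and judges clinically whether efficacy would have been affected. SAP 4.2 makes the per-protocol set (DBJPP) a sensitivity analysis of the primary endpoint. It lets the team decide before unblinding not to run that analysis if there are few relevant major deviations.

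**The concern.** The lead-in states the unit of the limits (a day's total) and the rows state another (one dose, repeatable up to five times a day). Both cannot describe the same figures. This is an operative safety limit for subjects aged 2 to under 18, so a site has to know which wording it is working under.

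The same wording also defines what counts as breaking the rescue rule. Two monitors who read the appendix differently could record the same use as compliant and as a deviation.

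**Working it through.** There is no stated daily total to reproduce, because the rows contain none. The check is to work out the daily maximum that each wording implies.

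**Inputs** (all from the opioid table in Appendix 5): the upper mg/kg figure *u*, the per-dose cap *c*, and the limit of 5 doses a day. Body weight *w* is an assumption, used only for illustration.

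**Formulas**

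- Lead-in governs, so the listed amount is the day's total: daily maximum = min(*u* × *w*, *c*).
- Row units govern, so the listed amount is one dose: daily maximum = 5 × min(*u* × *w*, *c*).
- Ratio = 5. Weight and agent cancel.

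**Daily maximum once the cap applies**

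| Agent | *u* (mg/kg) | *c* (mg) | Weight at which the cap applies, *c*/*u* | Lead-in governs | Rows govern |
|---|---|---|---|---|---|
| Morphine | 0.5 | 15 | 30 kg | 15 mg/day | 5 × 15 = 75 mg/day |
| Hydromorphone | 0.08 | 2 | 25 kg | 2 mg/day | 5 × 2 = 10 mg/day |
| Codeine | 1.0 | 60 | 60 kg | 60 mg/day | 5 × 60 = 300 mg/day |
| Oxycodone | 0.15 | 5 | 33.3 kg | 5 mg/day | 5 × 5 = 25 mg/day |

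**Below the cap** (morphine, assumed weights)

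- 12 kg: 0.5 × 12 = 6 mg/day against 5 × 6 = 30 mg/day.
- 20 kg: 0.5 × 20 = 10 mg/day against 5 × 10 = 50 mg/day.

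**What this does to classification.** Take an assumed 20 kg child given two 10 mg morphine doses in one day, 20 mg in total. Against a 10 mg daily total this is a breach. Against 10 mg per dose and five doses a day it is within the rule.

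**Does other text settle it?**

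- The back-reference for subjects on a listed background opioid speaks of total limits. That fits the lead-in, and it also fits a per-dose cap multiplied by five. It inherits the ambiguity without resolving it.
- The acetaminophen paragraph in the same appendix uses the same layout (amount per dose, number of doses in 24 hours) but carries no daily-total label. That supports taking the rows as written. It also shows that the label is not a drafting convention of the appendix.
- Section 5.9 sends the reader to Appendix 2 for rescue therapies. Appendix 2 contains no opioid rule.

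**The case against.** The strongest reply is that there is no real ambiguity. Each row gives an amount per dose, a cap per dose and a maximum number of doses, which is a complete rule. To reach the lower figures a reader must disregard the per-dose unit twice in every row. The lead-in could even be read loosely, as saying that these elements together determine the day's total. Most of this stands: a wrong label is the simplest explanation. It does not remove the point, because the label is part of the sentence that grants the permission and no other text says that the rows prevail.

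A second reply is that Section 5.8 already requires allowed concomitant medication to be locally approved and at a standard-of-care dose, so Appendix 5 is not the only constraint on prescribing. That is correct and lessens the practical exposure. It does not tell anyone what the protocol limit is.

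Three stronger readings are tempting and are not supported:

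- **That the 30 mg morphine-equivalent ceiling contradicts the table.** The ceiling equals neither morphine figure (30/15 = 2; 75/30 = 2.5). But it covers subjects already on a short-acting background opioid that is not among the four listed. It is also expressed as oral morphine, whereas the morphine row gives no route. Different limits for different agents and groups may be a clinical choice, and the two need not match.
- **That the back-reference to total limits is a second conflict.** It is compatible with either reading.
- **That a rescue breach removes a subject from the per-protocol set.** SAP 9.4 requires a case-by-case clinical judgment that efficacy was affected. A breach leads to review, and exclusion does not follow automatically.

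**Conclusion.** The lead-in and the rows of the opioid table contradict each other in unit. The implied daily maxima differ by a factor of exactly five for all four agents: 15 against 75 mg, 2 against 10 mg, 60 against 300 mg and 5 against 25 mg. The factor rests on no assumption about weight; only the 12 kg and 20 kg illustrations do. The lead-in is probably mislabelled, but the text does not settle it, and the rule for subjects on a listed background opioid carries the same uncertainty. No view is taken here on which limit is clinically right.

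The statistical consequence is limited. The reading decides who has broken the rescue rule. That feeds only case-by-case review for a supportive per-protocol analysis which may not be run.

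A reader might infer that the primary result is at risk, and the documents do not support that. SAP 4.1.1 defines the primary set (DBJAS) by randomization, at least one double-blind dose and polyarticular course JIA. Protocol 9.2.1 ties the endpoint to flare and to discontinuation of study treatment. Neither depends on the rescue dose. The detailed primary-analysis text in the SAP is blacked out, so this rests on the visible text.

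The reason to act is the clarity of a paediatric safety limit and consistent recording of deviations.

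**What to change.** Issue a clarification letter for Appendix 5 that reconciles three pieces of text: the lead-in, the four rows, and the back-reference for subjects on a listed background opioid. For each agent, the per-dose limit and the per-day limit should each be stated once and should agree, and the back-reference should point to whichever is meant. Which limit to adopt is the sponsor's clinical decision. The separate ceiling for other background agents can stay as it is.

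Use that single rule when rescue deviations are classified under SAP 9.4, and settle it before unblinding, since SAP 4.2 fixes membership of the per-protocol set by then. The same letter could correct the Section 5.9 cross-reference so that it leads to Appendix 5.

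The cost is a few words. Sample size, visits, endpoints and the primary analysis do not change.

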***For subjects who ARE on stable, background opioid therapy:***

- They may NOT add a second opioid agent for rescue;
- If their background medication is 1 of the 4 listed above, they may, within the above maximum total dosage limits, increase the dosage for up to 10 consecutive days for rescue purposes.
- If their background medication is a short acting (half-life <5 hrs) opioid that is not one of those listed above, they may increase the dosage for up to 10 consecutive days (up to a total daily dose which must not exceed the potency equivalent of 30 mg of orally administered morphine for rescue purposes).
- Sustained release opioid formulations (eg, OxyContin®, MS Contin®) and opioids with half-lives greater than 5 hours (eg, methadone, propoxyphene) may NOT be USED for rescue medication or increased for rescue purposes.

Intravenous or intramuscular corticosteroids, biologic response modifiers and DMARDs other than those specified as allowed DMARDs ([Appendix 1](#)) are not allowed during this study. Intra-articular corticosteroids may be given in no more than two joints, in a cumulative dose of no more than 80 mg methylprednisolone or its equivalent in any 6 month study period. Injections should be avoided for 6 weeks before any study visit. Injected joints

will also be considered as having their pre-injection status (tender/painful and swollen) for the remainder of the trial.

Acetaminophen/paracetamol is not permitted as a part of combination products such as over-the-counter “cold remedies” or in combination with opioids if the acetaminophen/paracetamol dose will exceed 2.6 gm/day. Subjects who require rescue for more than 10 consecutive days should be considered for allowed JIA medication adjustments or discontinued from the trial. In addition, subjects should not be dosed with rescue acetaminophen/ paracetamol or opioids during the 24 hours prior to a study visit. Baseline stable acetaminophen/ paracetamol or opioids should NOT be discontinued in advance of study visits.

**Subjects should avoid dosing with rescue intervention within 24 hours prior to a study visit unless indicated for subject safety and individual case management at the discretion of the investigator.**

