## SCHEDULE OF ACTIVITIES

The schedule of activities (SOA) table provides an overview of the protocol visits and procedures. Please refer to [Section 6](#) (Study Procedures) and [Section 7](#) (Assessments) of the protocol for detailed information on each procedure and assessment required for compliance with the protocol. The investigator may schedule visits (unplanned visits) in addition to those listed on the schedule of activities, in order to conduct evaluations or assessments required to protect the well-being of the subject.

For Investigative Sites in Germany Only: The degree of burden and the risk threshold should be assessed at each scheduled visit as outlined in [Appendix 10](#).

Protocol Activity	Screening	Day 1 	Week 2	Week 4	Week 8, 12	Week 18	Week 20, 24, 28, 32, 36, 40	Week 44 (EOS) or Early Termination 
			Day 14 (±3 days)	Day 28 (±3 days)	Day 56, 84 (±3 days)	Day 126 (±3 days)	Day 140, 168, 196, 224, 252, 280 (±3 days)	Day 308 (±3 days)
Informed Consent/Assent	X							
Medical History, Family History	X							
Uveitis Assessment 	X						X (Day 168, Week 24 only)	X
Prior/Concomitant Medications	X	X	X	X	X	X	X	X
Complete Physical Examination 	X					X		X
Targeted Physical Examination 		X	X	X	X		X	
Vital Signs, Height, Weight 	X	X	X	X	X	X	X	X
Tanner Stage Assessment		X						X
Assessments to be Faxed/Emailed to the Centralized Coordinating Center (CCC):								
JIA Disease Status Worksheet Including:	X	X	X	X	X	X	X	X
Uveitis Status Assessment	X	X	X	X	X	X	X	X
Duration of Morning Stiffness Assessment	X	X	X	X	X	X	X	X
Signs and Symptoms of Systemic Disease (sJIA Only)	X	X	X	X	X	X	X	X
JIA Joint Assessment (Swelling, Pain on Motion and/or Tenderness, Limitations of Motion)	X	X	X	X	X	X	X	X
Physician's Global Evaluation of Overall Disease Activity	X	X	X	X	X	X	X	X
Childhood Health Assessment Questionnaire (CHAQ)	X	X	X	X	X	X	X	X
Child Health Questionnaire (CHQ) (Not required by the CCC)		X		X		X		X
Disease Flare Assessment (According to the PRINTO/PRCSG Criteria and confirmed by the CCC)	X	X	X	X	X	X	X	X

Protocol Activity	Screening	Day 1 	Week 2	Week 4	Week 8, 12	Week 18	Week 20, 24, 28, 32, 36, 40	Week 44 (EOS) or Early Termination 
			Day 14 (±3 days)	Day 28 (±3 days)	Day 56, 84 (±3 days)	Day 126 (±3 days)	Day 140, 168, 196, 224, 252, 280 (±3 days)	Day 308 (±3 days)
Subjects with Enthesitis-Related Arthritis (ERA) Only:								

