## **5.8. Concomitant Treatment(s)**

A subject who is receiving an allowed concomitant medication for any reason must be on a locally-approved medication and dose that is considered standard-of-care for the treated indication. Medications taken after informed consent is obtained but before the first dose of study medication will be documented as prior medications. Medications taken after the first dose of study drug has been administered will be documented as concomitant medications.

Examples of medications that are prohibited from use during subject participation, due to potential for drug interactions or confounding of data interpretation, are listed in [Appendix 4](#), Prohibited Concomitant Medications. Topical administration (eg, cutaneous, ophthalmic, or intravaginal) of these concomitant medications, which are prohibited if administered

systemically, is allowed in the study. Disallowed and allowed non-biologic and biologic DMARDs are listed in [Appendix 1](#). If a subject requires (in the opinion of the investigator) treatment with one of the disallowed agents, the subject should be discontinued from the study.

Subjects will continue on their stable background arthritis therapy (see Inclusion Criterion 2), which can include nonsteroidal anti-inflammatory drugs (NSAIDs), cyclooxygenase-2 (COX-2) inhibitors, methotrexate (not to exceed 25 mg/wk or 20 mg/m^2/week [whichever is lower]) (see [Appendix 1](#)), and corticosteroids (at a maximum dose of 0.2 mg of prednisone equivalent per kilogram per day or 10 mg per day, whichever is lower). Subjects taking methotrexate must be taking folic acid or folinic acid in accordance with local standards.

For subjects with psoriatic arthritis refer to Inclusion Criterion 2 and Exclusion Criterion 25 for concomitant treatments that are allowed or prohibited (see [Appendix 1](#)). See [Appendix 2](#) for instructions on permitted adjustments in concomitant JIA therapies during the study.

Herbal supplements are not allowed and must be discontinued for at least 4 weeks prior to first dose of study drug.

Any experimental or prohibited therapy must be discontinued for at least 4 weeks or 5 half-lives (whichever is longer) prior to the first dose of study drug (see [Appendix 1](#)). No investigational compounds, other than tofacitinib may be taken during participation in this study.

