### **5.9. Rescue Therapy**

Refer to [Appendix 2](#) for permitted JIA rescue therapies.

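### Appendices 2 and 5 set different intra-articular steroid ceilings below 40 kg, and Appendix 5's 6-week timing advice cannot be followed in the double-blind phase if visits are kept

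*Protocol*

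**What the plan says.** **Appendix 2 (Permitted Adjustments In JIA Therapies), item 4.** "Intra-articular steroids should be administered in a total dosage of no more than 2 mg/kg (up to 80 mg") of methylprednisolone equivalent, per 6 months. No more than two joints may be injected in 6 months, and "individual joints should not be injected any more frequently than once in a 6-month period". On scoring: "Injected joints will be considered active joints for the remainder of the study and for efficacy assessments".

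**Appendix 5 (Rescue Therapy), text after the opioid rules.** Up to two joints may be injected, "in a cumulative dose of no more than 80 mg methylprednisolone or its equivalent in any 6 month study period". There is no mg/kg term and no per-joint frequency limit. On timing: "Injections should be avoided for 6 weeks before any study visit". Injected joints keep the status they had before injection, described as tender or painful and swollen, until the trial ends.

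**Cross-references.** Section 5.8 cites Appendix 2 "for instructions on permitted adjustments in concomitant JIA therapies during the study". Section 5.9, titled Rescue Therapy, cites Appendix 2 "for permitted JIA rescue therapies". No visible body section cites Appendix 5, and no text says which appendix takes precedence.

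**Visits.** In the Schedule of Activities the double-blind phase starts at Day 126, continues at "Day 140, 168, 196, 224, 252, 280 (±3 days"), and ends at Day 308, also ±3 days.

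**SAP.** The last visible item in Section 9.4 covers background medication changed against the protocol, and includes rescue medication used against the protocol. Section 4.2 uses such deviations to define the per-protocol set (DBJPP), and lets the team decide before unblinding whether to run that analysis.

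**The concern.** The protocol gives two upper limits for the same injection, and only one of them depends on weight. A site treating a child under 40 kg can find two different maximum amounts, depending on which appendix it opens. This is a large part of the intended population: five of the six dosing bands in Table 2 lie below 40 kg, and the study targets at least 20 subjects aged 2 to <6 years.

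Appendix 5 also permits injections while advising a 6-week gap before any visit, in a phase where visits come roughly every 4 weeks.

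The main stake is a clear pediatric steroid limit. The statistical stake is smaller. Whether an injection counts as against the protocol bears on the Section 9.4 deviation review, and the visible text offers two ceilings to judge it by. The documents give no expected injection frequency.

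**Working it through.** **1. Ceilings**

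Inputs: Appendix 2 ceiling = min(2 mg/kg × weight, 80 mg); Appendix 5 ceiling = 80 mg; both per 6 months. They cross at 80/2 = 40 kg. From 40 kg both appendices give 80 mg.

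The weights come from the Phase 1 JIA study described in the protocol: 13.9 kg is the lowest weight (Section 1.2.2); 17.3 and 32.4 kg are the medians for ages 2 to <6 and 6 to <12 years (Appendix 7, Results); 38.4 kg is the top of the second weight quartile (Appendix 7, Figure S5 note). The 10 kg row is the lower edge of a Table 2 dosing band and lies below the Phase 1 range.

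| Weight (kg) | Appendix 2 (mg) | Appendix 5 (mg) | Ratio | 80 mg as mg/kg |
|---|---|---|---|---|
| 10 | 2 × 10 = 20 | 80 | 4.0 | 8.0 |
| 13.9 | 27.8 | 80 | 2.9 | 5.8 |
| 17.3 | 34.6 | 80 | 2.3 | 4.6 |
| 32.4 | 64.8 | 80 | 1.2 | 2.5 |
| 38.4 | 76.8 | 80 | 1.04 | 2.1 |
| 40 | 80 | 80 | 1.0 | 2.0 |

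Since the second quartile ends at 38.4 kg, about half of the 26 Phase 1 subjects were in the range where the ceilings differ. That sample had near-equal age cohorts (8, 9 and 9), so the share need not carry over to this trial, whose weight mix is not given.

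**2. Timing**

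Six weeks is 42 days. An injection is taken to follow the advice if the next visit is at least 42 days later.

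- Run-in visits on Days 1, 14, 28, 56, 84 and 126: nominal gaps 13, 14, 28, 28 and 42 days.
- Double-blind visits on Days 126, 140, 168, 196, 224, 252, 280 and 308: one gap of 14 days, then six of 28.
- Widest double-blind gap with ±3-day windows: 28 + 6 = 34 days, below 42. Even with the ±7-day window that applies only to the uveitis examination, it is 28 + 3 + 7 = 38.
- Days 126 to 307 are 182 days. None is at least 42 days before the next visit: 0 of 182.
- In the run-in, only Day 84, after that visit, qualifies on nominal days. With the widest windows (Week 12 visit as early as Day 81, Week 18 visit as late as Day 129) the range is Days 81 to 87, since 129 − 42 = 87.

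A missed visit would change this. On nominal days, missing Week 20 alone leaves a 42-day gap, so only Day 126 qualifies. Missing any one of Weeks 24 to 40 leaves a 56-day gap, so 56 − 42 + 1 = 15 days qualify. These are departures from the schedule, not the plan.

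**3. Deviation review**

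Take 50 mg in a 17.3 kg subject. It is below 80 mg, so within Appendix 5, and above 34.6 mg, so outside Appendix 2. The visible text does not say which of the two readings the Section 9.4 review should use.

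**4. Scoring of injected joints**

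Appendix 2 calls an injected joint active; Appendix 5 gives it its earlier status. For a swollen joint these agree, because swelling alone makes a joint active under Section 7.1.1. This is a wording difference only.

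**The case against.** The two ceilings are both upper limits, and an amount within the lower one satisfies both. Sections 5.8 and 5.9 both route sites to Appendix 2. That appendix also requires sponsor project-team approval when a safety-related change goes beyond its limits, so it reads as the operative text. The SAP 9.4 item covers background and rescue medication alike, so the 50 mg example could be reviewed under either label, and the outcome rests on clinical judgment about whether efficacy was affected. The 6-week wording is advice, which can coexist with a permission. Both appendices fix the scoring of injected joints for the rest of the study, so an injection cannot improve the active joint count whenever it is given. Finally, the deviation review feeds only a supportive set.

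Most of this stands, and it limits the consequence: no effect on the primary analysis is shown. It does not remove the inconsistency. A cross-reference is not a precedence rule. Appendix 5 is current text, listed in the document history among the places touched by Amendment 6. A site that follows Section 5.9 literally reaches Appendix 2, which contains none of the acetaminophen or opioid rescue limits. The approval route in Appendix 2 covers safety reasons only. Fixed joint scoring does not extend to the other core-set variables, such as the global ratings, although no effect on those is shown either. Advice that no kept double-blind visit schedule can meet still needs correcting.

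**Conclusion.** The concern holds. The stated ceilings differ at every weight below 40 kg, by 2.3-fold at 17.3 kg and 2.9-fold at 13.9 kg, and are equal from 40 kg. If visits are kept, no double-blind injection can follow the 6-week advice. In the run-in only Day 84 can, or Days 81 to 87 at the widest windows.

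The ceiling result is exact arithmetic on the two texts. The timing result assumes that scheduled visits take place within ±3 days. How often this would matter is unknown, because neither injection frequency nor this study's weight mix is given.

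The primary set (DBJAS) does not depend on the deviation review. The statistical reach is limited to the supportive DBJPP set, which may be dropped, and one SAP 9.4 item is redacted. The correction should be made mainly because the point concerns a steroid limit in children.

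**What to change.** Reconcile Appendix 2, Appendix 5, Section 5.9 and the visit schedule so that the protocol contains:

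- one intra-articular ceiling;
- one statement on how often a single joint may be injected;
- one timing statement that is consistent with the visit schedule;
- one description of how injected joints are scored.

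Correct Section 5.9 so that it names every appendix that applies to rescue. Apply the reconciled text in the SAP 9.4 deviation review before unblinding. Which dose, interval or clinical rule applies is for the sponsor to decide.

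The cost is a clarification letter or amendment wording, with no new data, visits or procedures. Whether any SAP wording must also change cannot be judged, because much of its derivation text is redacted.
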